### **8.3.5 Pregnancy**

Details of pregnancies in female partners of male patients will be collected after first exposure to trial product and until the end of trial (follow-up) visit.

If a female partner of a male patient becomes pregnant **and** the outcome of the pregnancy is abnormal, the investigator should inform Novo Nordisk within 14 calendar days of learning of the abnormal outcome and should follow the procedures outlined in [Appendix 4](#).

### **8.3.6 Disease-related events and/or disease-related outcomes not qualifying as an AE or SAE**

The following disease-related events (DREs) are common in patients with haemophilia B and can be serious/life threatening:

- Bleeding episodes

#### **Bleeding episodes**

Because bleeding episodes are typically associated with the disease under study, they will not be reported according to the standard process for reporting of AEs/SAEs, even though the episodes may meet the definition of an AE/SAE. These episodes will be recorded in the patient diary and eCRF. These DREs will be monitored by Novo Nordisk on a routine basis.

Note: The bleeding episode must be recorded and reported both as a DRE and as an AE/SAE if one of the following applies:

- The event is, in the investigator's opinion, of greater intensity, frequency, or duration than expected for the individual patient.
- The investigator considers that there is a reasonable possibility that the event was related to treatment with the IMP.
- The event is considered life-threatening (see [Appendix 4](#) for definition of life-threatening).
- The event results in death.

### **8.3.7 Adverse event of special interest**

Please refer to Section [8.3](#) and [Appendix 3](#).

### **8.3.8 Technical complaints**

Technical complaints will be collected for all products listed on the technical complaint form.

Instructions for reporting technical complaints can be found in [Appendix 5](#).

In order for Novo Nordisk to perform a complete investigation of reported SAEs, Novo Nordisk might ask the investigator to complete a technical complaint form.

## **8.4 Treatment of overdose**

Accidental overdose must be reported as a medication error. Intentional overdose must be reported as misuse and abuse, please refer to Section [8.3](#) and [Appendix 3](#) for further details.

In the event of an overdose, the investigator should closely monitor the patient for overdose-related AEs/SAEs.

For more information on overdose, also consult the current version of the nonacog beta pegol investigator's brochure.[22](#)

## **8.5 Pharmacokinetics**

Patients in Arm B (PPX) will be administered a single i.v. bolus injection of 40 IU/kg of nonacog beta pegol at Visits 2 and 5. The pharmacokinetic sessions extend over 168 hours after dosing. After completion of the pharmacokinetic sessions, the patients will return to PPX treatment with the next visit in line.

Patients must not have received current FIX product for at least 96 hours prior to the administration of trial product for the single-dose pharmacokinetic session at Visit 2 (i.e. a wash-out period of at least 96 hours must be applied before Visit 2).

There is no wash-out period for the steady-state pharmacokinetic session at Visit 5. However, administration of trial product at Visit 5 should be approximately 168 hours after the previous nonacog beta pegol dose.

Patients must not be actively bleeding during the pharmacokinetic sessions.

The pharmacokinetic endpoints (see Section [3.2.2.3](#)) will be based on assessments performed from 1 hour prior to and up to 168 hours after administration of nonacog beta pegol at Visits 2 (single-dose pharmacokinetic assessments) and 5 (steady-state pharmacokinetic assessments) (see the flowchart for pharmacokinetic assessments in [Table 1-1](#)).

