## 1.2 Flowchart

Procedure	Protocol section	Screening	Baseline	Treatment period								End of treatment	Discontinuation of treatment	Surgery j
				V1	V2	V3	V4	V5	V6	V7 a	V8 b			
Visit														
Timing of visit		-2 weeks	0	4 weeks	8 weeks	12 weeks	20 weeks	28 weeks	36 weeks	44 weeks	50 weeks			30 days
Visit window		-7 days		±7 days	±7 days	±7 days	±7 days	±7 days	±7 days	±7 days	±7 days	+56 days c		+5 days
Informed consent and demography	10.1.3	X												
Informed consent obtained date		X												
Legal or authorised representative		X												
Demography		X												
Eligibility criteria	5.1 5.2	X	X											
Medical history/concomitant illness	8.2	X	X											
Details of haemophilia		X												
Haemophilia treatment and bleed history		X												
Concomitant medication	6.5	X	X	X	X	X	X	X	X	X	X	X		X
Body measurements	8.2.2	X	X			X		X			X	X		
Body weight		X	X			X		X			X	X		
Height		X						X d			X d			
Body mass index		X												
Vital signs	8.2.3	X	X			X		X			X	X		

Procedure	Protocol section	Screening	Baseline	Treatment period								End of treatment	Discontinuation of treatment	Surgery j	End of trial (follow-up)
				V1	V2	V3	V4	V5	V6	V7 a	V8 b				
Visit															
Timing of visit		-2 weeks	0	4 weeks	8 weeks	12 weeks	20 weeks	28 weeks	36 weeks	44 weeks	50 weeks			30 days	
Visit window		-7 days		±7 days	±7 days	±7 days	±7 days	±7 days	±7 days	±7 days	±7 days	+56 days c		+5 days	
Physical examination	8.2.2	X	X			X			X				X	X	
ECG	8.2.4	X											X	X	
Neurological examination	8.2.2.1	X	X			X			X				X	X	
Target joint assessment	8.2.2	X													
Discontinuation criteria	7.1		X	X	X	X	X	X	X	X	X				X
Adverse events	8.3			X	X	X	X	X	X	X	X		X	X	X
Adverse events requiring additional data	8.3			X	X	X	X	X	X	X	X		X	X	X
Medication error, misuse and abuse	8.3			X	X	X	X	X	X	X	X				X
Technical complaint	8.3.8			X	X	X	X	X	X	X	X				X
Bleeding episode	8.1.1		X e	X	X	X	X	X	X	X	X		X		X
Laboratory assessments	8.2.5 App. 2	X	X	X	X	X	X	X	X	X	X		X		X

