**Figure 4-1 Overview of trial design**

A total of 30 patients will be included in the trial and a minimum of 24 patients must complete the trial. The trial will have two arms: Arm A (on-demand/PPX treatment arm) and Arm B (PPX treatment arm including single-dose and steady-state pharmacokinetic assessment). Patients will not be randomised to Arm A and Arm B. Whether a patient will be in Arm A or Arm B is the choice of the patient and the investigator and will be decided at the screening visit. A minimum of 12 patients in each of the two treatment arms must complete the trial.

In Arm A (on-demand/PPX), the on-demand treatment period will be 28 weeks. For a patient in Arm A, 30 EDs to nonacog beta pegol in the entire trial must be fulfilled to complete the trial (including treatment of bleeds during the on-demand period as well as scheduled once-weekly PPX doses and treatment of breakthrough bleeds during the PPX period).

In Arm B (PPX), 50 EDs to nonacog beta pegol (including treatment of breakthrough bleeds) and 50 weeks in trial must be fulfilled to complete the trial. One single-dose and one steady-state pharmacokinetic profile will be obtained in patients in Arm B. The single-dose pharmacokinetic profile will start at first dosing (Visit 2), while the steady-state pharmacokinetic profile will be obtained at Visit 5. The steady-state pharmacokinetic profile may be postponed but must be conducted between Visit 5 and Visit 9.

In both treatment arms, the screening period will be 2 weeks (+7 days) and the follow-up period will be 30 days (+5 days).

The duration of the trial for each individual patient will be up to 64 weeks, i.e. 2 weeks screening period, up to 58 weeks treatment period (only applicable in Arm A in case a patient has no or few bleeds during the trial) and 30 days follow-up period.

The clinical efficacy assessment of nonacog beta pegol in the treatment of bleeding episodes will be based on the treatment of all bleeding episodes in Arm A and Arm B (including specific information on target joints as defined at baseline). The haemostatic response to nonacog beta pegol will be assessed by the patient/caregiver using a four-point scale (excellent, good, moderate and none response) by counting excellent and good as success and moderate and none as failure. Amount and number of injections of nonacog beta pegol per bleeding episode will also be recorded.

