#### **4.1.6 Treatment during screening and follow-up periods**

Patients should follow their normal treatment regimen during the screening and follow-up periods. Treatments will not be reimbursed by Novo Nordisk during these periods. Bleeds that occur during

the screening and follow-up periods should be treated as per standard local practice and will not be assessed.

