### 7.1 Discontinuation of trial treatment

A patient who does not fulfil the eligibility criteria (inclusion/exclusion criteria) must not be included in the trial. Inclusion in violation of any of the eligibility criteria is non-compliant with Good Clinical Practice (GCP) procedures and must be reported to the sponsor without delay. This will be handled as an important protocol deviation, and the independent ethics committee (IEC)/institutional review board (IRB) and regulatory authorities must be notified according to local requirements. If there are no safety concerns for the patient, trial treatment may be continued or resumed at the discretion of the investigator after agreement with the sponsor's global medical expert.

A patient may be discontinued from treatment with nonacog beta pegol at the discretion of the investigator due to a safety concern.

The trial product must be discontinued, if any of the following applies for the patient:

1. Simultaneous use of an approved or non-approved investigational medicinal product in another clinical trial.
2. Haemostasis not achievable with nonacog beta pegol: The bleed cannot be controlled after 48 hours using adequate doses of nonacog beta pegol.
3. FIX inhibitors  $\geq 0.6$  and  $\leq 5$  BU, as confirmed by re-testing by central laboratory, which makes treatment (prophylaxis and/or treatment of bleeding episodes) with nonacog beta pegol clinically ineffective (see Section [8.6.2](#)).
4. FIX inhibitors  $>5$  BU as confirmed by re-testing by central laboratory.
5. Severe allergy/anaphylaxis to the trial product.
6. Use of coagulation factors FVIII, FIX and FVII-containing products other than nonacog beta pegol and other FIX-containing products such as fresh frozen plasma or cryoprecipitate (**Exception:** FIX is allowed until 120 hours before visit 2).
7. Incapacity or unwillingness to follow the trial procedures.

8. Use of anti-coagulants such as heparin and vitamin-K antagonists (heparin is allowed for sealing of central venous access devices according to local practice).
9. Use of emicizumab.
10. Anti-fibrinolitics except for local/topical use. Use of single systemic doses is allowed after careful benefit-risk evaluation.

See the flowchart in Section [1.2](#) for data to be collected at the time of treatment discontinuation (discontinuation of treatment visit; Visit 10A) and follow-up and for any further evaluations that need to be completed.

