### **7.2.1 Replacement of patients**

Patients who discontinue trial product or withdraw from trial will not be replaced.

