#### 8.1.1 Bleeding episodes

From Visit 2 (inclusion of the patient) and during the entire trial period, all treatment-requiring bleeding episodes (also referred to as 'bleeding episodes' or 'bleeds') must be entered by the patient or caregiver in the patient's diary. In case a patient is unable to enter a bleeding episode in the diary or is hospitalised, the investigator will report the bleeding episode in the eCRF (refer to Sections [8.3.6](#) and [8.7](#) for reporting in the diary and eCRF).

If a patient experiences a bleeding episode at home, treatment with nonacog beta pegol should be initiated irrespective of severity of the bleeding episode (refer to Section [8.8](#) for training in home treatment). If the bleed is mild/moderate, the treatment responsibility is with the patient, patient's caregiver(s) and/or the investigator. For severe bleeding episodes, the treatment responsibility is always with the investigator, and the patient should contact the site for further instructions.

Treatment of severe bleeding episodes should be initiated as soon as possible by the patient or caregiver. It is the responsibility of the investigator to assess the severity of the bleeding episodes and to ensure that all data is recorded correctly in the patient's diary.

Any discrepancy observed by the investigator or site staff must be documented in the patient's medical record and the patient must be retrained on completion of the diary, if required.

A need for haemostatic rescue therapy with another FIX product will be assessed by the investigator via phone or during the site visit. Patients treated with FIX products other than nonacog beta pegol must be discontinued from treatment with nonacog beta pegol (exception: the patient's current FIX product is allowed until 120 hours before Visit 2).

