1.2 Trial design

This trial is a multi-centre, open-label phase 3b trial evaluating the clinical efficacy, safety (including immunogenicity) and pharmacokinetics of nonacog beta pegol during on-demand and for prophylactic treatment in Chinese patients aged 12-70 years with haemophilia B and a FIX activity of $\leq 2\%$.

A total of 30 patients will be included in the trial (15 in each treatment arm) and a minimum 12 patients in each of the two treatment arms must complete the trial. The trial will have two arms: Arm A (on-demand/PPX treatment arm) and Arm B (PPX treatment arm including single-dose and

steady-state pharmacokinetic assessment). Patients will not be randomised to Arm A and Arm B. Whether a patient will be in Arm A or Arm B is the choice of the patient and the investigator and will be decided at the screening visit. The duration of the trial for each individual patient will be up to 64 weeks, i.e. 2 weeks screening period, up to 58 weeks treatment period (only applicable in Arm A in case a patient has no or few bleeds during the trial) and 30 days follow-up period.

Please refer to protocol section 4.1 for more details.

2 Statistical hypotheses

No confirmatory hypotheses are planned to be tested due to the low number of patients to be included in this trial.

3 Sample size determination

No formal sample size calculations have been performed. Based on meeting communication with CDE, a total number of 24 Chinese patients to complete this trial is assessed to be sufficient to evaluate efficacy and safety in the Chinese population, considering that data are also available from the global pivotal trial NN7999-3747, which included Asian patients. In order to account for withdrawn patients, 30 patients will be started on trial product (15 patients in Arm A [on-demand/PPX] and 15 patients in Arm B [PPX]).

All 15 patients in Arm B will participate in the pharmacokinetic evaluation to ensure that at least 12 patients will complete single-dose and steady-state pharmacokinetic profiles.

4 Analysis sets

All patients exposed to nonacog beta pegol in this trial will be included in the full analysis set (FAS) and the safety analysis set (SAS).

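### Section 8.5 accepts a 96 h FIX wash-out before Visit 2, but sections 7.1 and 8.1.1 make FIX use within 120 h of Visit 2 a ground for mandatory discontinuation

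*Protocol*

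**What the plan says.** Protocol section 8.5 sets the wash-out for Arm B patients before the single-dose PK session. It gives the 96 h figure twice in one sentence, the second time as "a wash-out period of at least 96 hours must be applied before Visit 2".

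Section 7.1 lists the conditions under which trial product must be stopped. Criterion 6 is the use of other FIX-containing products, with one exception: "FIX is allowed until 120 hours before visit 2". Section 8.1.1 also requires discontinuation of patients treated with another FIX product, and words the exception as "the patient's current FIX product is allowed until 120 hours before Visit 2".

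Four other provisions bear on the point:

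- Section 4.1.6, on the weeks before Visit 2: "Patients should follow their normal treatment regimen during the screening and follow-up periods". It does not mention a wash-out.
- The flowchart in section 1.2 has a row "Discontinuation criteria" that is ticked from Visit 2 onwards.
- Section 4.1: "A minimum of 12 patients in each of the two treatment arms must complete the trial". SAP section 3: "In order to account for withdrawn patients, 30 patients will be started on trial product", of whom 15 are in Arm B.
- Section 7.2.1: "Patients who discontinue trial product or withdraw from trial will not be replaced".

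**The concern.** The protocol gives two different limits for the same act. Section 8.5 is where staff preparing the PK session would look for the wash-out, and it tells them that 96 h is enough. A site that relies on it can dose a patient whom section 7.1 then says must come off trial product. The site would have to discontinue a patient who followed the PK section, or keep him on treatment against the discontinuation section.

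Section 7.1 allows treatment to continue after an eligibility violation if there is no safety concern. It offers no such route for its numbered discontinuation criteria.

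At stake are protocol compliance and, possibly, the number of Arm B completers. A patient discontinued at Visit 2 cannot reach the 50 exposure days that section 4.1 requires for completion, and he cannot supply the steady-state profile.

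**Working it through.** This is mainly a comparison of texts. The plan has no figure of its own to reproduce.

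**1. The rules side by side.**

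| Time from last FIX dose to Visit 2 dosing | Section 8.5 | Sections 7.1 (criterion 6) and 8.1.1 |
|---|---|---|
| under 96 h | not allowed | discontinue |
| 96 h to under 120 h | allowed | discontinue |
| 120 h or more | allowed | allowed |

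Only the middle row conflicts. Its width is 120 − 96 = 24 h.

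**2. Does criterion 6 reach back before the first dose?** Yes. Its exception is expressed in hours before Visit 2, so the criterion covers use in that period, and the flowchart has the criteria checked at Visit 2.

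**3. Can a patient fall in the band?** Yes. Section 4.1.6 keeps patients on their usual regimen through screening.

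**4. How many?** The documents give no prior dosing interval, so no forecast is possible. The following is illustration only:

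- Sites apply 120 h, or move the dose: 0 patients.
- Assume prophylaxis every 72–96 h and a last dose timed by section 8.5 alone: 24/96 = 25% to 24/72 = 33% of such patients. If all 15 came from prophylaxis, 15 × 0.25 = 3.75 to 15 × 0.333 = 5.0.
- On-demand patient at the inclusion minimum of 6 bleeds a year: 6/365.25 = 1.6% for a given 24 h.
- Margin in Arm B: 15 − 12 = 3.

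**5. Effect on the single-dose profile.** Section 2.2 gives a 5-fold half-life ratio of nonacog beta pegol to standard FIX products. No absolute value is given. Assuming 70–110 h for nonacog beta pegol, the previous product has 14–22 h. The fraction of its peak that remains is 2^(−t/half-life):

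- at 96 h: 2^(−96/14) = 0.9% to 2^(−96/22) = 4.9%
- at 120 h: 2^(−120/14) = 0.3% to 2^(−120/22) = 2.3%

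Both are small. SAP section 5.4.3 and protocol section 9.4.3.4 also exclude Visit 2 profiles with pre-dose FIX above 5%.

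**6. Side check: a bleed dose shortly before the steady-state session.** The trough analysis (SAP section 5.4.1.4) drops values less than 14 days after a bleed dose. The PK analysis (SAP section 5.4.3) has no matching rule. Because the weekly dose keeps its planned day (section 4.1.3), an extra dose 8–13 days earlier still meets the one-week spacing in section 8.5. With a one-compartment model, k = ln 2/half-life and an extra 40 IU/kg dose d days before, the relative rise in AUC(0–168h) is exp(−24dk) × (1 − exp(−168k)):

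| Assumed half-life | d = 8 | d = 13 | mean, d = 8–13 |
|---|---|---|---|
| 75 h | 13.4% | 4.4% | 8.2% |
| 110 h | 19.5% | 9.1% | 13.8% |

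The bleeding rate of 1.90 [1.27; 2.84] per year in section 2.2 pools adult/adolescent and paediatric trials, so it is approximate here. It gives 1.90 × 6/365.25 = 3.1% of patients with such a dose. The expected shift in the group mean is 0.031 × 8.2% = 0.26% to 0.031 × 13.8% = 0.43%. At the upper limit, 2.84 × 6/365.25 × 13.8% = 0.64%.

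**The case against.** The strongest reply is that the sections can all be met together. The 96 h is a minimum and 120 h is simply stricter, so a site that reads the whole protocol has no conflict. A patient found inside the band before dosing need not be lost. Section 4.1 gives the screening period a 7-day allowance, so Visit 2 can move by the 24 h at most that is needed. Eligibility and discontinuation criteria are both on the Visit 2 checklist, and nothing requires dosing before they are checked. The no-replacement rule bites only once a patient has received trial product.

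All of this stands, and it limits the consequence. It does not remove the inconsistency: a site that doses at, say, 100 h has followed an operative instruction and still triggers a mandatory stop.

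A reader might infer from step 4 that Arm B could lose four or five patients and miss its minimum of 12. The documents do not support that. It needs every patient to come from prophylaxis, an assumed dosing interval, every site to read section 8.5 alone, no check of section 7.1 before dosing, and literal enforcement afterwards.

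A reader might also infer that the single-dose PK results would be biased. The residual activity is small under the assumed half-lives, and the 5% pre-dose exclusion is a backstop.

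**Conclusion.** The protocol is wrong as written on one number. Section 8.5 accepts a wash-out that sections 7.1 and 8.1.1 treat as a ground for mandatory discontinuation, over a 24 h band and for Arm B only. This conclusion rests on the text and needs no assumption.

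The number of patients affected is unknown, and it is zero if sites wait 120 h or delay dosing. The defect concerns conduct and compliance. The primary endpoint analysis does not depend on it, and the effect on PK is limited. It is still worth correcting, because the arm has a margin of only three and the correction is nearly free.

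The steady-state side check is minor. A reader might infer that the PK analysis needs its own 14-day exclusion rule after a bleed dose. The figures do not support one: the expected group-mean AUC shift for a 40 IU/kg dose is below 1%, in a descriptive secondary analysis. The pre-lock review may already exclude exceptional outlier profiles, and a sensitivity analysis on all observed data follows any exclusion. These percentages rest on the assumed half-life and a one-compartment model.

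**What to change.** In protocol section 8.5, replace 96 hours with 120 hours in both places, so that it agrees with criterion 6 in section 7.1 and with section 8.1.1. The SAP needs no change. The only cost is a wait of up to 24 h more than section 8.5 now asks, which section 7.1 already demands.

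Optional, and not needed for the point: add a sentence to section 8.5 that if an extra bleed dose falls 8–13 days before the planned steady-state session, the session should preferably move by one weekly dose, within the Visit 5 to Visit 9 range that section 4.1 permits. Days 8–13 then become days 15–20. On the step 6 formula the AUC excess falls to 2.8–6.8% at day 15 and 0.9–3.2% at day 20, so the gain is partial. A new bleed in the added week could delay the session again. No new exclusion rule should be added: it would remove profiles from an arm where protocol section 9.2 wants at least 12 complete ones.

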### **8.5.1 Visit 2 for patients undergoing pharmacokinetic assessment**

Visit 2 should take place as soon as possible upon confirmation of eligibility approximately 2 weeks after the screening visit (Visit 1). Overnight stay is not required during the pharmacokinetic evaluation.

At Visit 2, the patients will receive their first dose of nonacog beta pegol (40 IU/kg) at the site and 7 pharmacokinetic samples will be taken during the following 168 hours. The lines must be flushed immediately after administration of the trial product. The blood sample taken pre-dose may be taken from the same arm as the one used for nonacog beta pegol administration. The blood sample taken 30 min post-dose must not be taken from the same vein as used for administration of nonacog beta pegol.

If a bleeding episode occurs between trial product administration and the last pharmacokinetic blood sample at 168 hours, the patient must contact the site and preferably come to the site for treatment with nonacog beta pegol. Further blood sampling for pharmacokinetic will be stopped. If the patient experiences a bleeding episode at home that requires immediate treatment, or if the investigator judges it as necessary, the patient must treat himself at home with nonacog beta pegol.

Assessments at Visit 2 are outlined in Section [1.2](#) and additional assessments and sampling for patients having pharmacokinetics evaluated are outlined in [Table 1-1](#).

The second dose of nonacog beta pegol will be administered at the site after the last pharmacokinetic sample at 168 hours post-dose is taken.

